7.2 Projected Accrual and Attrition Rates

Participants will be recruited from participating centres across the UK. At least 22 hospital units in England and Scotland will contribute to the total, with more sites joining the study if required to randomise 4,150 women within one year. Thus it will be necessary for the trial to achieve a mean recruitment rate of 189 women per centre (approximately 16 participants at each site per month), but local numbers will also be affected by the size of the unit and local population coverage.

7.3 Statistical Analyses

The analysis will be by intention to treat. Every attempt will be made to gather data on all women randomised, irrespective of compliance with the treatment protocol. Point estimates, 95% confidence intervals and p-values

ISRCTN: 14163439

from two-sided tests will be calculated for the outcome measures. A Statistical Analysis Plan will be drawn up prior to any analysis and reviewed by the independent Data Monitoring Committee (DMC).

7.3.1 Interim Analyses

Interim analyses will be conducted on behalf of the DMC (please refer to section 8.4). These will be considered together with a report of the Serious Adverse Events. The DMC will meet before recruitment commences, and thereafter at least annually. Effectiveness and futility criteria will be ratified by the DMC. The DAMOCLES charter will be adopted by the DMC and will include a specific remit for reviewing emerging data from other trials.

7.3.2 Primary Endpoint Analysis

The primary endpoint will be the proportion of women randomised who experience a live birth beyond 34 weeks. The denominator of this proportion will be all women randomised, and the numerator will be those women who proceed to have a live birth beyond 34 weeks. We will use a log-binomial regression model to calculate the relative risk and 95% confidence intervals. Minimisation variables (maternal age, BMI, fetal heart activity, gestation at presentation, and amount of bleeding) will be included as covariates. The p-value from the associated chi-squared test will be produced and used to determine statistical significance.

7.3.3 Secondary Endpoint Analyses

Dichotomous secondary outcomes (e.g. miscarriage rate, survival at 28 days) will be analysed in the same fashion as the primary outcome. Time from randomisation to live birth will be analysed by log-rank test with a Cox Proportional Hazard (PH) model also built if the assumptions of proportionality are met. Fetuses/babies will be censored at the last time-point known to be alive if the final outcome is not known. Standard methods will be used to analyse other outcomes (e.g. t-tests for continuous outcomes such as birth weights). Appropriate summary statistics split by group will be presented for each outcome (e.g. proportions/percentages, mean/standard deviation or median/interquartile range).

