3.3.2 Randomisation Methods and Stratification Variables

Participants will be randomised online via a secure internet facility in a 1:1 ratio through an Integrated Trial Management System. A "minimisation" procedure using a computer-based algorithm will be used to avoid chance imbalances in important stratification variables. Strata used in the minimisation will be:

- Age (<35, ≥35 years).
- Body Mass Index (BMI) (<30, ≥30).
- Fetal heart activity (present, absent).
- Estimated gestation at presentation (<42, ≥42 days).
- · Amount of bleeding (PBAC [Pictorial Bleeding Assessment Chart] score ≤2; ≥3).

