6.2 Secondary Outcome Measures

- Gestation at delivery.
- · Ongoing pregnancy at 12 weeks (range 11 to 13 weeks) of gestation.
- · Miscarriage rate (delivery before 24 weeks of gestation).
- Survival at 28 days of neonatal life.
- Chromosomal and congenital abnormalities.
- · Adverse events.
- · Antenatal complications (such as pre-eclampsia, growth restriction).
- If delivery ≥24 weeks, mode of delivery, birth weight, arterial and venous cord pH, APGAR scores, and resuscitation data.
- Neonatal outcomes: ventilation support and neonatal complications (such as infection, retinopathy of prematurity, necrotising enterocolitis and intraventricular haemorrhage).

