7 ACCRUAL AND ANALYSIS

7.1 Sample size

We plan to randomise 4,150 women in total (2075 participants each in the progesterone and placebo arms). To detect a Minimally Important Difference (MID) of 5% in live birth beyond 34 weeks (from 60% baseline live birth rate to 65%), for an alpha error rate of 5% and 90% power), it will be necessary to randomise a total of 3940 women to the intervention and placebo groups. However, assuming and adjusting for a 5% attrition rate, the total number of participants required will be 4,150.

The Minimally Important Difference of 5% was defined following consultations amongst healthcare practitioners, patients and representatives of patient bodies as well as through a survey of clinicians. However, it should be noted, this difference is much smaller than what could be expected from the existing literature (please refer to section 2.1.1 and particularly to **Figure 1**), which has shown that the risk of miscarriage is halved with progesterone therapy (RR 0.53, 95% CI: 0.39, 0.73). If the actual difference in live birth is greater than 5%, then the study will have a power greater than 90% to detect that difference; if this is the situation, the DMC and TSC will be able to consider an early finish to recruitment.

The 60% baseline (control) event rate is derived from audits from 2 of the participating units (Imperial College London, and the Royal Infirmary Edinburgh). However, because there is previously published evidence to suggest a higher control event rate, we have provided sample size (**Table 3**) and power (**Table 4**) calculations in the tables below for higher control event rates. We believe it is prudent to work on the assumption of a lower control event rate for power calculation, because this in fact represents a worse-case scenario. The sample size requirements of the lower event rate provide sufficient (and in fact higher) power for a higher control event rate. All the power calculations noted above use two-sided binominal testing.

Table 3 Sample sizes with varying levels of control event rate, all assuming a 5% absolute difference, 5% attrition rate, 90% power and p=0.05

Control rate (%)	Intervention rate (%)	Total sample size required
55	60	4,320
60	65	4,150
65	70	3,880
70	75	3,520
75	80	3,090
80	85	2,550

Table 4 Power with varying levels of control event rate, if sample size is fixed at 4,150, all assuming 5% absolute difference, 5% attrition rate and p=0.05

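### Time to live birth is set for a plain log-rank/Cox analysis with no rule for known pregnancy losses, and two intended benefits push its hazard ratio in opposite directions

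*Protocol*

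**What the plan says.** Protocol section 7.3.3 fixes the endpoint and the test: "Time from randomisation to live birth will be analysed by log-rank test with a Cox Proportional Hazard (PH) model also built", the Cox model being conditional on proportional hazards. The only rule for leaving the risk set is "Fetuses/babies will be censored at the last time-point known to be alive if the final outcome is not known". Nothing is said about a miscarriage, stillbirth or termination that is known to have happened. No cumulative incidence or competing-risks method is named, and the text does not say whether a hazard ratio above or below 1 is favourable.

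Section 6.2 does not list time from randomisation to live birth. The nearest listed outcome is "Gestation at delivery". Section 2.1.3 counts better gestation at birth among the hoped-for benefits. Section 7.1 plans for a change "from 60% baseline live birth rate to 65" per cent in live birth beyond 34 weeks.

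**The concern.** Loss makes a later live birth impossible. Section 6.2 defines miscarriage as ending before 24 weeks, so it precedes almost every live birth. At the planning rates, up to 40% of the placebo arm and 35% of the progesterone arm do not reach the primary outcome, and most of these will be losses.

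Two things follow. First, a plain log-rank or Cox analysis removes a woman from the risk set at her loss, so preventing losses does not register in the hazard ratio. Second, the trial hopes for both more live births and later birth. More live births raise the cumulative incidence of live birth; later birth lowers its hazard. One hazard ratio then mixes two benefits of opposite sign.

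At stake is whether a secondary result reads as benefit, no effect or harm. A convention that the protocol leaves open could decide that, and it could be chosen after the data are seen.

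**Working it through.** **Inputs from the protocol.** Rates of 60% and 65% (section 7.1); "for an alpha error rate of 5% and 90% power" and "All the power calculations noted above use two-sided binominal testing" (7.1); "Participants will be randomised online via a secure internet facility in a 1:1 ratio" (3.3.2); "assuming and adjusting for a 5% attrition rate" (7.1); entry at about 5 to 12 weeks (4.1.5); miscarriage before 24 weeks (6.2).

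**The plan's own figure.** The protocol gives no figure for this analysis, so the check starts from its sample size. With pooled variance and no continuity correction:

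n per arm = [1.960 × √(2 × 0.625 × 0.375) + 1.2816 × √(0.60 × 0.40 + 0.65 × 0.35)]² / 0.05² = (1.3419 + 0.8762)² / 0.0025 = 1,968.1, rounded up to 1,969.

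The total is 3,938 (stated 3,940). Then 3,938 / 0.95 gives 4,146 (stated 4,150). The plan reproduces. Evaluable women per arm: 4,150 × 0.95 / 2 = 1,971.

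**What the hazard ratio must be if birth timing is unchanged.** Take 60% and 65% as the live-birth proportions p, let every loss precede every live birth, and let G(t) be the same distribution of live-birth times in both arms.

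- Losses censored: once losses have left, the risk set holds only women who go on to a live birth. The hazard is g/(1 − G) in both arms, so the ratio is 1 whatever p is.
- Losses kept at risk: the hazard is p·g/(1 − p·G). The ratio runs from 0.65/0.60 = 1.083 at the start to (0.65/0.35)/(0.60/0.40) = 1.857/1.500 = 1.238 at the end. An average somewhat above 1.1 is expected.

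**Simulation.** Two simulations with 1,971 women per arm used different timing assumptions, none of them from the protocol. Both took entry as uniform over 5 to 12 weeks.

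- S1: losses exponential with mean 3 weeks after entry; births at mean 39.1 weeks, SD 1.5; 1,500 trials per scenario.
- S2: losses exponential with mean 2.5 weeks; births at about 39.3 weeks, SD 1.5, with 7% preterm; 500 trials per scenario.

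Hazard ratios for live birth, progesterone v placebo, at 60% v 65%:

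| Birth delay on progesterone | Simulation | Losses censored | Losses kept at risk |
|---|---|---|---|
| none | S1 | 1.002 (5–6% significant) | 1.135 (88% significant) |
| none | S2 | 0.997 (2.2% above 1, 2.4% below) | 1.131 (86.0% above 1) |
| 1 day | S1 | 0.943 | 1.119 |
| 1 day | S2 | 0.950 (24.0% below 1) | 1.117 (78.2% above 1) |
| 2 days | S1 | 0.889 (81% below 1) | 1.101 |
| 3 days | S1 | 0.835 | 1.087 |
| 3 days | S2 | 0.853 (98.8% below 1) | 1.089 (57.6% above 1) |

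**Other scenarios (S2).**

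- Without a delay, control rates of 70% and 80% give 0.999 and 0.997 with losses censored, and 1.130 and 1.133 with losses kept at risk.
- Live birth at 60% in both arms with births 3 days later gives 0.854 (censored) and 0.964 (kept at risk). Later birth alone lowers the ratio under either convention.
- If half of the 5-point gain were born preterm (2.5/65 = 3.8% of progesterone live births), the ratios rise to 1.033 and 1.151. More preterm birth moves the ratio the way more live births do. Section 6.3 names a rise in preterm birth as a possibility.

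**The case against.** The strongest reply is that section 7.3.3 does not fix the version that fails. Its censoring rule is confined to unknown outcomes, a confirmed miscarriage is a known outcome, and keeping such women at risk is compatible with the text. Handled that way, the planned benefit shows clearly. How losses enter the risk set is also a detail commonly left to the SAP, and section 7.3 promises one before any analysis.

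Much of this stands. A reader might infer that the analysis cannot show benefit; the 1.13 with losses kept at risk refutes that. The missing rule alone would be a matter for the SAP. What remains is the choice that the protocol has made: a log-rank/Cox analysis, blind to prevented losses in its usual form, on a measure that later birth pulls the other way under either convention.

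Three further limits also stand:

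- The 40% and 35% are upper bounds on loss, since the remainder includes live births at or before 34 weeks and Tables 3 and 4 allow control rates up to 80%.
- Starting the clock at randomisation across 5 to 12 weeks might look like bias. It is not: allocation is randomised and gestation at presentation is a minimisation factor. It affects precision only.
- Prevented losses are captured directly by the primary outcome (7.3.2) and the binary miscarriage analysis (7.3.3).

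**Conclusion.** The point holds for one secondary analysis and is minor to moderate. At the planned effect with unchanged birth timing, the hazard ratio is about 1.00 if losses are censored and about 1.13 if they stay at risk. With an assumed delay of 2 to 3 days it is about 0.84 to 0.89 or about 1.09 to 1.10, so the same data fall on opposite sides of 1. The value of 1.00 follows from losses preceding births and does not depend on the simulated distributions; the other values do.

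A reader might go further and infer that a treatment working exactly as planned would look harmful. The protocol does not support that. With unchanged timing the live-birth ratio is 1.00 or 1.13; falling below 1 requires both censoring at loss and later births, and no size for a delay is given. Nor is the trial's main conclusion at risk, because the primary outcome is a proportion of all women randomised.

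**What to change.** Replace the sentence in section 7.3.3, and carry the change into the SAP before any unblinded analysis:

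- Live birth is the event. Known loss (miscarriage, stillbirth, termination) is a competing event, not censoring. Censoring is kept for unknown final outcomes only.
- Report cumulative incidence of live birth by arm, compared by Gray's test or by a Fine-Gray model adjusted for the minimisation variables. Give the curves prominence, since the ratio with losses kept at risk is not constant over time (1.083 to 1.238 above).
- Report gestation at delivery among live births separately, as the listed section 6.2 outcome.
- State which direction of each estimate is favourable.

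The cost is wording and minor analysis work. Table 2 in section 6.5.2 already collects miscarriage, live birth and gestation at delivery.

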2.1.3 Aims and Objectives

The primary aim of the PRISM trial is:

To test the hypothesis that in women presenting with vaginal bleeding in the first trimester, progesterone (400 mg vaginal capsules, twice daily), started as soon as possible after a scan has demonstrated a visible intrauterine gestation sac, and continued to 16 completed weeks of gestation, compared with placebo, increases maternities with live births beyond 34 completed weeks by at least 5%.

Additional secondary aims are:

- 2. To test the hypothesis that progesterone improves other pregnancy and neonatal outcomes, including gestation at birth and survival at 28 days of neonatal life.
- 3. To test the hypothesis that progesterone, compared with placebo, is not associated with serious adverse effects to the mother or the neonate, including chromosomal anomalies in the newborn.

- 4. To explore differential or subgroup effects of progesterone in prognostic subgroups, including age, fetal heart activity, gestation at presentation, amount of bleeding and body mass index.
- 5. To perform a cost-effectiveness analysis, with cost per additional birth over 34 weeks of gestation from an NHS and Personal Social Services perspective as the primary analysis. We will also model longer term outcomes to the extent the data permit.

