6.3 Health Economic Evaluation

If progesterone is shown to be an effective intervention to reduce the risk of miscarriage in pregnant women with early pregnancy bleeding, then it is likely that important cost implications will be seen for the healthcare sector. For example, progesterone may help to maintain the pregnancy for a longer period, avoiding miscarriage but

possibly instead leading to an increase in the number of cases of preterm birth. Preterm birth is associated with high costs both in the short-term (neonatal care) and longer-term; for instance, the potential impact on neurological development may lead to requirements for special needs assistance through early childhood, schooling and even adulthood. Given this situation, the economic evaluation will take the NHS and Personal Social Services (PSS) perspective of the societal costs.

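### Section 7.3.3 gives known pregnancy losses no place in the log-rank/Cox analysis of time to live birth, and neither natural way of handling them yields a hazard ratio that can be read as benefit or harm

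*Protocol*

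**What the plan says.** Section 7.3.3 of the protocol fixes the method for the time outcome: "Time from randomisation to live birth will be analysed by log-rank test with a Cox Proportional Hazard (PH) model also built", the Cox model being conditional on proportionality. The event is live birth and the clock starts at randomisation. One censoring rule follows: "Fetuses/babies will be censored at the last time-point known to be alive if the final outcome is not known". Nothing is said about a pregnancy whose outcome is known and is not a live birth, and no competing-events method is named.

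Three other places bear on how the result would be read:

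- Section 2.1.3 sets a secondary aim: "To test the hypothesis that progesterone improves other pregnancy and neonatal outcomes, including gestation at birth and survival at 28 days". Among surviving pregnancies, a better gestation at birth normally means a later birth, so an HR below 1.
- Section 6.3 raises the possibility that progesterone avoids miscarriage while "possibly instead leading to an increase in the number of cases of preterm birth".
- Section 7.1 plans on an improvement in live birth beyond 34 weeks "from 60% baseline live birth rate to 65"%.

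**The concern.** A miscarriage, stillbirth or termination makes a later live birth of that pregnancy impossible. It is a competing event, and a common one here. A log-rank test on live birth needs a rule for these women, and the stated rule does not reach them. There are two natural completions. Losses can be censored when they happen, as if those women could still deliver, or they can be kept in the risk set to the end of follow-up.

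The choice changes what is estimated. The first compares birth timing among pregnancies that survive, a group selected after randomisation. The second mixes the chance of a live birth with its timing. In both, earlier delivery raises the hazard of live birth, although the protocol counts better gestation at birth as a gain. What is at stake is a reported HR and p-value whose sign a reader cannot interpret.

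**Working it through.** **Planning figures.** Inputs from section 7.1: 60% against 65%, "for an alpha error rate of 5% and 90% power", and "All the power calculations noted above use two-sided binominal testing"; 1:1 allocation from section 3.3.2. With pooled variance under the null:

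n per arm = [1.960·√(2·0.625·0.375) + 1.2816·√(0.60·0.40 + 0.65·0.35)]² / 0.05² = (1.3419 + 0.8762)² / 0.0025 ≈ 1,968.1, so 1,969.

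The total is 3,938, and 3,938/0.95 gives 4,146. The protocol's 3,940 and 4,150 reproduce after rounding. It states no figure for the time-to-live-birth analysis.

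**Share of women affected.** The complements of 60% and 65% are 40% and 35%. They refer to live birth beyond 34 weeks and so include live births before then. The share with no live birth at all is smaller. Tables 3 and 4 go up to 80% against 85%, that is 20% and 15% without the outcome.

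**Algebra.** Let p be the probability of live birth, and G (density g) the distribution of time to live birth among those who have one. Suppose losses precede nearly all births; section 6.2 defines miscarriage as before 24 weeks.

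- *Rule A, losses censored.* The hazard once losses have occurred is p·g / [p·(1−G)] = g/(1−G). The probability p cancels, so fewer losses leave HR = 1.
- *Rule B, losses kept at risk.* The hazard is p·g / (1−p·G). With the same G in both arms and p of 0.60 and 0.65, the ratio starts at 0.65/0.60 = 1.083 and ends at (0.65/0.35)/(0.60/0.40) = 1.238. An overall guide is ln(0.35)/ln(0.40) = 1.0498/0.9163 = 1.146. Shifting G earlier also raises the hazard.

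**Simulation.** 1,971 women per arm, 300 to 400 trials per scenario, two-sided 5% log-rank test, entry uniform over 5 to 12 weeks. Two sets of timing assumptions, neither from the protocol:

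- Set 1: 62% live birth on placebo; losses exponential with mean 14 days after entry, before 24 weeks; births 92% Normal(277, 9) days and 8% uniform over 196 to 259 days.
- Set 2: 60% live birth on placebo; losses exponential with mean 3 weeks, before 24 weeks; births Normal(39.2, 1.8) weeks.

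| Progesterone effect | Rule A | Rule B |
|---|---|---|
| Live birth +5 points, same timing (both sets) | HR 1.00; 3-5% rejected | HR about 1.13; 87-89% significant above 1 |
| No effect on loss, births 3 to 3.5 days earlier (both sets) | HR 1.17-1.18; 98-99% above 1 | HR 1.04-1.05; about 19% above 1 |
| No effect on loss, births 7 days earlier (A: set 2; B: both sets) | HR about 1.39; 100% above 1 | HR 1.09-1.10; 56-69% above 1 |
| +5 points, births 3 to 3.5 days later (A: both sets; B: set 2) | HR 0.85; 98% below 1 | HR 1.08; 50% above 1 |
| +5 points, births 7 days later (set 2) | HR 0.73; 100% below 1 | HR 1.03; 16% above 1 |
| −5 points, births 7 days earlier (set 2) | HR 1.39; 100% above 1 | HR 0.95; 0.7% above 1 |

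With no effect at all (set 2), rejection was 4.3% under Rule A and 5.5% under Rule B, so the tests are calibrated. The pattern persists at higher control rates. At 80%, the 5-point gain gives HR 1.00 under Rule A and 1.13 under Rule B, and births 7 days earlier give 1.16 under Rule B.

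**The case against.** The strongest reply has four parts.

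1. *The literal text does not censor known losses.* A known miscarriage has a known outcome, so the rule points towards keeping it at risk. The planned gain is then seen in 87-89% of trials, and the case with more losses and earlier births is almost never significant above 1. This stands. The 98% results belong to Rule A, which the protocol does not state. But Rule B still raises the HR for earlier births, so it does not make the direction readable.

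2. *The effects are separated elsewhere.* The primary outcome and the miscarriage rate are analysed as proportions with relative risks, gestation at delivery is a listed outcome, and summaries by group are promised for each. This stands and limits the damage to one secondary analysis.

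3. *A statistical analysis plan can set the coding of losses.* It can, and such a plan is not shown here. But the protocol has already fixed the test, the event and a partial censoring rule, and either natural completion leaves the HR hard to interpret.

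4. *The sizes are assumed.* They are. Moving the whole birth distribution is also not the same as adding preterm births, which section 6.3 mentions only as a possibility. The directions follow from the algebra, not from the chosen distributions.

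**Conclusion.** The point holds as a defect of one secondary analysis. Under Rule A the HR cannot register fewer losses (1.00 for a 5-point gain) and answers only to birth timing (about 1.17 for 3 days earlier). Under Rule B fewer losses (about 1.13) and earlier births (about 1.04 to 1.10 for 3 to 7 days) both move it above 1. These sizes rest on the assumed loss and birth timing.

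A reader might infer more than the protocol supports:

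- *That the HR rises equally for fewer losses and earlier births.* It does not. Under Rule A it ignores losses, and under Rule B the sizes differ.
- *That 35-40% of women are expected to have no live birth.* That range is an upper bound, for the reason given in the working.
- *That the trial would report harm as benefit.* The protocol never says that an HR above 1 is favourable, and the most striking figures need a censoring rule it does not contain.
- *That the protocol expects miscarriages to be exchanged for preterm births.* Section 6.3 only allows for it.
- *That the main conclusion is at risk.* It is not, because the primary outcome does not use this analysis.

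**What to change.** In section 7.3.3, replace the log-rank/Cox sentence with two items:

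1. Cumulative incidence of live birth and of pregnancy loss by gestational age, over all women randomised, each treated as a competing event for the other, with between-arm differences and 95% confidence intervals at stated gestations (24, 34 and 37 weeks, for example).
2. Gestational age at birth among live births, reported separately as a distribution by arm and labelled descriptive, because it conditions on survival after randomisation.

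Keep a censoring rule for unknown outcomes, and say explicitly that miscarriage, stillbirth and termination are events of the competing type. If a Cox model is retained, state how known losses enter it and that its HR is not a measure of benefit.

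The cost is wording in the protocol and the matching text of the analysis plan. The outcomes and gestation at delivery are already to be collected under Table 2 in section 6.5.2, so no new data and no change to the sample size are needed.

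### Continuous secondary outcomes are given an unadjusted t-test although the trial minimises on five factors and adjusts its primary and dichotomous outcomes for them (minor, free improvement)

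*Protocol*

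**What the plan says.** Section 3.3.2 lists five minimisation factors (age, BMI, fetal heart activity, gestation at presentation, amount of bleeding), introduced by "Strata used in the minimisation will be". Section 7.3.2 carries them into the primary model: "Minimisation variables (maternal age, BMI, fetal heart activity, gestation at presentation, and amount of bleeding) will be included as covariates".

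Section 7.3.3 then treats the secondary outcomes in three ways:

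- Dichotomous: "Dichotomous secondary outcomes (e.g. miscarriage rate, survival at 28 days) will be analysed in the same fashion as the primary outcome". These are therefore adjusted.
- Time to event: "Time from randomisation to live birth will be analysed by log-rank test with a Cox Proportional Hazard (PH) model also built", the Cox model depending on proportionality. No covariates or strata are stated.
- Continuous: "Standard methods will be used to analyse other outcomes (e.g. t-tests for continuous outcomes such as birth weights". No covariates are stated.

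Section 6.2 sets the population for several of these outcomes: "If delivery ≥24 weeks, mode of delivery, birth weight, arterial and venous cord pH, APGAR scores, and resuscitation data". Section 7.3.3 does not say how a comparison in that subset should be read. The exclusion criteria in section 3.2.2 do not list multiple pregnancy.

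**The concern.** The protocol accepts that the minimisation factors belong in the analysis, then names for continuous outcomes a test that cannot include them, and gives no reason. Minimisation removes part of the chance variation between arms. An unadjusted test still counts that variation in its standard error, so its intervals are wider than they need be. This bears on the second and third aims in section 2.1.3, improved neonatal outcomes and absence of serious harm to the neonate: a less sensitive test makes a finding of no difference easier to reach.

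Two further points arise for the same outcomes. Birth weight is measured per baby, and a t-test across babies would treat twins as independent, which makes the standard error too small. And birth weight, cord pH and APGAR scores exist only for deliveries at 24 weeks or later. If progesterone works, it changes who enters that set. Section 6.3 itself anticipates that some avoided miscarriages may become preterm births, so a difference in mean birth weight could appear with no effect on growth.

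**Working it through.** **The plan's own figure.** The protocol gives no sample size or power for any continuous outcome. Its primary calculation (section 7.1: "from 60% baseline live birth rate to 65"%, "for an alpha error rate of 5% and 90% power", two-sided) can be reproduced with pooled variance and no continuity correction:

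- n per arm = [1.960·√(2·0.625·0.375) + 1.282·√(0.60·0.40 + 0.65·0.35)]² / 0.05² ≈ 1,969, total 3,938 (stated 3,940).
- 3,938/0.95 ≈ 4,146 (stated 4,150).

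The stated size is sound and nothing below changes it.

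**Cost of not adjusting.** Let R² be the share of outcome variance explained by the five factors. The protocol does not give it; the range 1% to 20% is assumed.

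- Width of the unadjusted interval relative to the adjusted one: 1/√(1−R²).
- Actual two-sided type I error of the t-test if the factors are fully balanced in the set analysed: 2·[1−Φ(1.960/√(1−R²))].
- Power of the t-test where the adjusted model has 80%: Φ(2.802 − 1.960/√(1−R²)).

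| R² (assumed) | Interval wider by | Type I error | Power |
|---|---|---|---|
| 1% | 0.5% | 0.049 | 79.7% |
| 5% | 2.6% | 0.044 | 78.5% |
| 10% | 5.4% | 0.039 | 76.9% |
| 20% | 11.8% | 0.028 | 72.9% |

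The type I column is the most conservative case. Birth weight is analysed in only part of the women minimised, so the forced balance is diluted. If a fraction f is retained at random, the true variance of the unadjusted difference is (1−f·R²) times what the t-test assumes. With f = 0.65, type I error is 0.046, 0.043 and 0.036 at R² of 5%, 10% and 20%. Simulated biased-coin minimisation on five binary factors (1,000 women, 6,000 runs, Monte Carlo error about 0.003) agrees: 0.042, 0.039 and 0.028 with everyone analysed, and 0.043, 0.045 and 0.034 with 65% retained. The interval widths against the adjusted model are unaffected by this dilution.

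**Selection into the 24-week set.** The protocol gives no rate for delivery at 24 weeks or later, so its 60% and 65% (live birth beyond 34 weeks) serve as a proxy.

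- Women followed up per arm: 4,150·0.95/2 ≈ 1,971.
- Deliveries: 1,971·0.60 ≈ 1,183 and 1,971·0.65 ≈ 1,281.
- Share of progesterone deliveries with no placebo counterpart: 0.05/0.65 = 7.7%.
- Shift in the arm mean = 0.077 × deficit, where the deficit (assumed) is how much lighter those babies are than the rest: 8 g at 100 g, 23 g at 300 g, 38 g at 500 g, 77 g at 1,000 g.
- Standard error = SD·√(1/1,183 + 1/1,281): 20 g at SD 500 g and 28 g at SD 700 g (SD assumed).

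The shift therefore ranges from well under one standard error to between about 2.7 and 3.8, depending wholly on a deficit the documents do not give.

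**The case against.** The strongest reply is that the t-test is introduced as an example of standard methods. Section 7.3 promises a statistical analysis plan before any analysis, and covariates, clustering and labelling are usual content for it. This stands in part: the t-test is not a binding rule for every continuous outcome, and the unseen plan may already do better. But it is the only method the protocol names for them, and a better one is available at no cost, so the example is worth changing.

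Four stronger readings are tempting, and the documents do not support them:

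- A reader might infer that every other model is adjusted. Only the primary and dichotomous secondary analyses are; the log-rank test and Cox model have no stated covariates.
- A reader might infer that the t-test is invalid after minimisation. For independent observations it errs on the conservative side, and only mildly at an R² of 5% to 10%.
- A reader might infer that the comparison is confined to survivors and is therefore wrong. The criterion is delivery at 24 weeks or later, which does not exclude stillbirths, and some such restriction is unavoidable for birth weight. The issue is interpretation.
- A reader might infer that a false signal of harm is to be expected, or that regression would prevent one. The size rests on assumed inputs, and five baseline factors remove the selection only so far as they explain it.

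It is also fair to say that dichotomous secondary outcomes, by following the primary, arguably already use all women randomised as the denominator. The twin point has no magnitude, because the protocol gives no multiple-pregnancy rate.

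**Conclusion.** The point holds as a minor inconsistency in the secondary analyses. The protocol's named method for continuous outcomes ignores factors that it minimises on and adjusts for elsewhere, and the time-to-event methods are also stated without them. For continuous outcomes the loss is modest: 2.6% to 5.4% in interval width at an assumed R² of 5% to 10%, and about 12% at 20%. The selection caution is separate: its size is uncertain and it calls for labelling. Neither the sample size nor the primary inference is affected. This is a low-severity improvement to consider.

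**What to change.** In section 7.3.3, or in the statistical analysis plan:

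1. Replace the t-test example with linear regression on arm plus the five minimisation variables.
2. Where the outcome is per baby, cluster standard errors on the mother.
3. Include the same variables in the Cox model, or stratify the log-rank test by them.
4. State that birth weight, cord pH, APGAR scores and the other outcomes limited to deliveries at 24 weeks or later are conditional on a post-randomisation event, and that they are read alongside outcomes in all women randomised. Do not present covariate adjustment as a cure for this selection.

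The cost is a few sentences and a few lines of code. No new data are needed: section 3.3.1 requires all baseline items before a trial number is issued, so the covariates should be complete.
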